Manchester University

University for the Common Good

Process Evaluation

Analysis Plan

FINAL Version 1.0

16 March 2021

 Date: 27 th April 2021
 Date: 27 th April 2021

Glossary of abbreviations

DMEC Data Monitoring and Ethics Committee HTA Health Technology Assessment NIHR National Institute for Health Research PMG Project Management Group TOPSY **T**reatment **O**f **P**rolapse with **S**elf-care pessar**Y** TSC Trial Steering Committee RCT Randomised Controlled Trial

1. Introduction

The NIHR HTA commissioning brief asked for an internal pilot study "to demonstrate the ability to recruit and randomise, and participants' adherence to allocated treatment, with clear stop/go criteria to the main trial". This document sets out how the process evaluation data will be collected, analysed and reported. Quantitative data where referred to will be analysed in line with the conventions laid out in the main trial Statistical Analysis Plan (SAP) except where stated otherwise.

TOPSY includes a nested process evaluation which runs alongside the main RCT. The process evaluation will collect and analyse qualitative and quantitative data about recruitment, intervention fidelity, participants' experiences of participating in the trial and adherence to trial protocols and group assignment. Findings will be reported to PMG, TSC, DMEC and HTA.

2. Our definition of 'on treatment'

For women self-managing their pessary, 'on treatment' is;

- If they are randomised to self-management;
- IF they have NOT discontinued pessary care (determined by the change of status form);
- If they have received the intervention;
- AND if they have answered Yes to question 2d (Pessary use questionnaire) "Have YOU inserted your pessary yourself in the last 6 months" at either 6,12 or 18 months"

For women in the standard clinic-based care arm of the study,

"On treatment" is:

- IF they are randomised to standard care;
- IF they have NOT discontinued pessary care (determined by the change of status form);
- AND if they have answered Yes to question 1 (Pessary use questionnaire) "Have you used a pessary for prolapse at any time in the last 6 months?" at least once at either 6, 12 and 18 months
- AND they have ticked NO to Q2d (Have you inserted your pessary in the last 6 months) at ALL time-points (6 12 and 18 months).

** Additional analysis – those who have answered yes to q2d at any time point who are in any group (standard care and self-management)

Additional analysis (to decide if standard care women are "on treatment"): If any data is missing we will assume they have answered No to Q2d

If any data is missing we will assume they have answered Yes to Q2d

3. Process evaluation

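### As written, on-treatment status needs three returned answers in standard care but one in self-management, and missing answers are varied only in standard care

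*SAP*

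**What the plan says.** SAP section 2 defines on-treatment status separately by arm. Both definitions turn on item Q2d of the pessary use questionnaire, which asks about self-insertion over the preceding six months.

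- **Self-management.** Besides allocation, receipt of the intervention and no recorded discontinuation, the rule is "AND if they have answered Yes to question 2d (Pessary use questionnaire"), and this may be "at either 6,12 or 18 months". One observed Yes is enough.
- **Standard care.** Besides allocation and no recorded discontinuation, she must report pessary use (question 1) "at least once at either 6, 12 and 18 months". The further condition is "AND they have ticked NO to Q2d (Have you inserted your pessary in the last 6 months) at ALL time-points", and the three visits are then listed.
- **Missing answers.** An additional analysis, introduced "to decide if standard care women are" on treatment, takes a missing Q2d as No. A second line, without a label of its own, reads "If any data is missing we will assume they have answered Yes to Q2d". Its natural scope is the standard-care introduction just above it.
- **Both arms.** One other additional analysis covers "those who have answered yes to q2d at any time point who are in any group (standard care and self-management"). It counts observed Yes answers and sets no rule for blanks.

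The section does not say how the main rule treats a blank.

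**The concern.** Adherence to allocation is one of the things this evaluation sets out to describe (SAP section 1), and section 2 is the document's only working definition of it. If the two arms need different numbers of returned questionnaires to qualify, an adherent standard-care woman can be classed off treatment for a blank that would not disqualify an equally adherent self-management woman. Standard care could then look less adherent for reasons unrelated to what the women did.

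Sensitivity analyses for missing answers should show how much this matters. Here they vary one arm only, and read literally one of them returns the main result unchanged.

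**Working it through.** The plan states no figure on this point, so there is none to reproduce.

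**Step 1. Which answer patterns qualify.** Each visit gives Yes, No or blank, so there are 3³ = 27 Q2d patterns. Applying the Q2d condition alone:

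| Arm and rule | Patterns that qualify | Change from literal main rule |
|---|---|---|
| Standard care, literal (No ticked at all three) | 1 | – |
| Standard care, missing = Yes | 1 | 0 |
| Standard care, missing = No | 2³ = 8 (no Yes anywhere) | 7 |
| Self-management, as written (any observed Yes) | 27 − 8 = 19 | – |
| Self-management, missing = No | 19 | 0 |
| Self-management, missing = Yes | 27 − 1 = 26 | 7 |

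In each arm the seven patterns that change are those with at least one blank and no Yes. So missing = Yes repeats the literal standard-care rule. The self-management rule already treats a blank as No, and its one informative variation, missing = Yes, is not planned.

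**Step 2. The other reading of the main rule.** If the requirement for all time points meant all answered ones, 7 patterns would qualify in standard care (8 less the all-blank one). Missing = Yes would then differ in 6 patterns, and missing = No in only the all-blank one. One of the two analyses is therefore redundant or nearly so on either reading.

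**Step 3. What is bracketed.** Within standard care, missing = No gives the largest on-treatment set and missing = Yes the smallest. For the difference, self-management minus standard care:

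- the smallest value pairs self-management with missing = No (its existing rule) and standard care with missing = No, which is planned;
- the largest value pairs missing = Yes in self-management with missing = Yes in standard care, which is not planned.

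**Step 4. Size.** Take a woman who follows her allocation throughout and answers truthfully whenever she returns a questionnaire. Let r be the return probability per visit, equal in both arms. The document does not give r, so 0.80 to 0.90 is an assumption. With returns independent across visits:

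- standard care, literal rule or missing = Yes: r³
- self-management: 1 − (1 − r)³

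| r | Standard care | Self-management | Gap (points) |
|---|---|---|---|
| 0.90 | 0.729 | 0.999 | 27 |
| 0.85 | 0.614 | 0.997 | 38 |
| 0.80 | 0.512 | 0.992 | 48 |

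Section 3.2 gives 340 women randomised but no arm sizes. Assuming 340 / 2 = 170 per arm, at r = 0.80 this is 170 × 0.992 ≈ 169 women classed on treatment against 170 × 0.512 ≈ 87.

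If each woman instead returns all of her questionnaires or none, both arms keep a fraction r and the gap is zero.

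Under missing = No, a standard-care woman needs only one returned questionnaire, for question 1. Her chance is then 1 − (1 − r)³, the same as in self-management, and the imbalance disappears.

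**The case against.** The case on the other side has real force.

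- **A reader might infer that the planned assumptions bracket nothing.** The document does not support that. They are introduced for standard care, and for a missing Q2d in that arm they give the two extremes. A lower bound that coincides with a strict main rule is still a lower bound. Only the between-arm difference is left open.
- **The duplication depends on the literal reading.** Section 2 is silent on blanks in the main rule, and the two assumptions may have been meant to supply that rule in two versions. That stands. It changes which analysis is the near-repeat, and it shows that the rule for blanks must be written down.
- **The planned missing = No analysis already removes the imbalance in required returns.** This also stands. The imbalance belongs to the literal main rule and to missing = Yes.
- **The two weaknesses do not peak together.** With independent returns the imbalance is large, but self-management loses only 0 to 1 of an assumed 170 adherent women, so varying that arm changes little. With all-or-none response, self-management losses matter but the imbalance is zero.
- **A reader might infer a biased treatment comparison.** No outcome comparison among on-treatment women is specified here. The mediation analysis in section 4.8 does not mention the flag, and the main trial SAP, to which it refers for its models, is not shown.
- **A reader might infer that the self-management set is nearly everyone who replied.** It is not. Women must also have received the intervention, not discontinued, and answered Yes at least once. The 0.99 figures apply to fully adherent women only.

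**Conclusion.** The point holds in a limited form. Followed as written, section 2 makes described adherence depend on questionnaire return differently in the two arms. One planned missing-data analysis is redundant or nearly so on either reading of the main rule. Because self-management is never varied, the largest between-arm difference compatible with the missing answers is not computed.

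The size is unknown. With assumed equal return rates of 0.80 to 0.90 per visit, the gap for fully adherent women is zero under all-or-none response and 27 to 48 percentage points under independent returns. It would be tempting to read the upper figures as a forecast of adherent standard-care women lost. They are not one, because neither the return rates nor their clustering within women are given.

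Severity is moderate: the document ties the flag to the description of adherence and to no outcome analysis.

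**What to change.** 1. Keep the definitions over 18 months: at least one Yes in self-management, no Yes in standard care. State that the main rule in both arms uses answered Q2d items only, with at least one answered, so that a blank is neither Yes nor No. Report women with no answered Q2d as unclassified, by arm.
2. Keep missing = No and missing = Yes for standard care, and label the arm on both lines.
3. Add missing = Yes for self-management. Missing = No there reproduces the section's existing rule and needs no new derivation.
4. Report the between-arm difference in adherence under the two extreme pairings: missing = Yes in both arms, and missing = No in both arms.

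Under the new main rule, missing = No in standard care differs only for women with every Q2d blank. It stays because it supplies one end of the range.

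The cost is SAP wording and re-deriving one flag, with somewhat wider reported bounds. No new data are needed.

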3.1 Research Questions

- 1) What are the:
 - a) barriers and facilitators to intervention¹ acceptability for Healthcare professionals (HCP)
 - b) barriers and facilitators to treatment² acceptability for TOPSY participating women
 - c) barriers and facilitators to treatment effectiveness
 - d) mediating factors impacting fidelity of intervention delivery
 - e) barriers and facilitators impacting on adherence for women treated with vaginal pessary
 - f) barriers and facilitators impacting on protocol adherence for the health professionals who treat women with pelvic organ prolapse
 - g) identify whether barriers and facilitators differ between randomised groups
- 2) Investigate women's experiences of
 - a) Self-management intervention
 - b) Standard Care intervention
 - c) Usual care out with the trial
 - d) Recruitment
 - e) Retention to the study and to trial arm
 - f) Treatment outcomes
- 3) Investigate healthcare professionals' experiences of
 - a) Self-management Intervention
 - b) Standard care intervention
 - c) Recruitment
 - d) Treatment outcomes for women with prolapse
- 4) To identify contextual factors
 - a) That help maximise recruitment
 - b) That create barriers to recruitment
 - c) that interact with intervention effectiveness
- 5. Describe fidelity to intervention delivery

6. What are factors influencing trial participation for women with pelvic organ prolapse using a pessary as treatment?

¹ Intervention refers to the self-management TOPSY teaching processes

² Treatment refers to both self-management intervention and standard care practices

3.2 Types of data

- 1. Audio-record self-management teaching sessions (21 audio-recordings)
 - 1-2 per centre
 - Time frame: June 2018 February 2020
- 2. Audio-record 2-week follow-up phone calls (34 audio-recordings)
 - 1-2 per centre
 - Time frame: June 2018 March 2020
- 3. Interviews with healthcare professionals (HCPs) (35 telephone interviews)
 - Recruiters (1 per centre) and healthcare professionals delivering the intervention (1 per centre); only 1 interview where HCP holds dual roles as recruiter and intervention deliverer
 - Time frame: August 2018 February 2020
- Interviews with randomised women (36 face-to-face interviews baseline (18 self-management, 18 standard care); and 23 18-month follow-up) and non-randomised women (20 telephone baseline interviews; and 18 18-month follow-up)

Time frame: August 2018 – April 2021

- 5. Intervention checklist, CRF 05 (n=156)
- 6. 2-week follow-up call, CRF 06 (n=145)
- 7. Main trial Questionnaires (340 women randomised at baseline)

4. Analysis method for each data source

The process evaluation researchers are blinded to all trial data, including the analysis element of this; however, they are unblinded for all qualitative process evaluation data to which the trial team is blinded.

Each data source will be analysed individually in the first instance to reach separate conclusions and findings then synthesised across data sources. All qualitative data sources will be transcribed verbatim and entered into NVivo for data management. All of the analysis described below will be undertaken by the process evaluation subgroup of grant-holders. Analysis will not be shared with the wider grant-holding group until the main trial findings are revealed.

4.1 Recordings of teaching sessions

Recordings will be transcribed verbatim. A priori developed analytic grid based on the intervention checklist and underlying philosophy will be applied to the verbatim transcripts. The grid will contain

explicit guidance as to what codes have to be applied in what circumstances. Data will be entered into SPSS. Data will be described with the appropriate descriptive statistics: mean and standard deviation (SD) for continuous outcomes (or medians and interquartile range for skewed data), and counts and percentages for dichotomous and categorical outcomes. For example, data from the self-management teaching session and two-week follow up call will be described with a particular focus on fidelity such as the percentage of women who have been able to 1) remove and 2) replace their pessary themselves.

4.2 Recordings of 2 week follow-up phone calls

Recordings will be transcribed verbatim. A priori developed analytic grid based on the 2 week followup phone call CRF will be applied to the verbatim transcripts. The grid will contain explicit guidance as to what codes have to be applied in what circumstances. Data will be entered into SPSS. Data will be described with the appropriate descriptive statistics: mean and standard deviation (SD) for continuous outcomes (or medians and interquartile range for skewed data), and counts and percentages for dichotomous and categorical outcomes. For the 2 week follow-up phone call will be described with a particular focus on fidelity such as the percentage of women who have been able to 1) remove and 2) replace their pessary themselves or those who needed an additional phone call.

4.3 HCP interviews

Interview recordings will be transcribed verbatim and analysed using a Thematic Framework analysis approach – summarised below (Ritchie et al, 2013).

- 1. Transcript uploaded to NVivo
- 2. Transcript read and re-read to familiarise with content
- 3. Develop initial framework
- 4. Apply framework to all HCP interviews (adjust/amend where necessary throughout data coding)
- 5. Intercoder reliability will be established by having second coder independently code 10% of transcripts
- 6. Data extracts reviewed.
- 7. Data summarised and displayed using framework tables.
- 8. Review of preliminary "findings" involving wider research study team and PPIs
- 9. Data described and explained
- 10. Summary and presentation of findings

4.4 Interviews with Randomised women

Each participant interviewed twice (baseline & 18-month) if not lost to follow-up, withdrawn or declining the second interview.

Interview recordings will be transcribed verbatim and analysed initially using Thematic Framework analysis and then within a case study approach (detailed below).

- 1. Transcript uploaded to NVivo
- 2. Transcript read and re-read to familiarise with content
- 3. Develop initial framework
- 4. Apply framework to all interviews (adjust/amend where necessary throughout data coding)
- Intercoder reliability will be established by having second coder independently code 10% of transcripts
- 6. Case summaries written
- 7. Theoretical propositions developed
- 8. Key features of data for each study condition group described
- 9. Comparison of study groups based on theoretical propositions.
- 10. Review of preliminary "findings" involving wider research study team and PPIs
- 11. Summary and presentation of findings

4.5 Interviews with non-randomised women

Each participant interviewed twice (baseline & 18-month) if not declining the second interview.

Interview recordings will be transcribed verbatim and analysed using Thematic Framework within a case study approach as detailed below.

- 1. Transcript uploaded to NVivo
- 2. Transcript read and re-read to familiarise with content
- 3. Develop initial framework
- 4. Apply framework to all interviews (adjust/amend where necessary throughout data coding)
- 5. Intercoder reliability will be established by having second coder independently code 10% of transcripts
- 6. Case summaries written
- 7. Theoretical propositions developed
- 8. Key features of data described
- Comparison of groups based on theoretical propositions (women can be either selfmanaging or receive standard care)

- 10. Review of preliminary "findings" involving wider research study team and PPIs
- 11. Summary and presentation of findings

Case study analysis (interview data with women - randomised and non-randomised)

Each case comprises one woman and all the data gathered about that woman.

This is a three-tailed case study with the tails representing intervention and control arms of the trial respectively, as well as women who declined participation in the trial but consented to the interview study alone. Women will have been purposively sampled to reflect participant diversity (age, new/existing user, centre and potentially severity of POP and type of pessary used). The maximum total sample size will be 56 cases (20 women who only consented to the interview study [non-randomised group], 18 women in the intervention arm and 18 in the control arm). Priority will be given to complete datasets (cases which have interviews for both time points) during the analysis process. A sampling table will be populated to monitor sample diversity during the recruitment progress.

Each woman will be asked to undertake 2 interviews throughout the study duration. The first interview will be conducted at baseline and the second after 18 months. This coincides with trial data collection at baseline and at 18 months (primary outcome). For randomised women, where possible both interviews will be carried out face-to-face. Due to the COVID-19 pandemic and subsequent restrictions, all face-to-face interviews were suspended and carried out via telephone to comply with new government regulations. For non-randomised women interviews will be by phone. For women randomised to self-management, where possible baseline interviews will occur prior to their self-management teaching appointment.

The Baseline interview will explore the woman's experience of POP and symptoms, current self-care, expectations of treatment and her experience of being recruited to the trial, and, where applicable, reasons for not consenting to the main trial but the interview study.

The 18-month interview will explore the woman's experience of self-management/standard pessary care, experience of being taught self-management (where applicable), obstacles and complications of pessary treatment, expectations of treatment over the long term, experience of participating in the trial and adherence to trial group.

Analysis will be on four interacting levels:

1. Individual interview (steps 1-5 in interview analysis)

An a priori coding scheme will be applied that focuses on core areas of interest and which will be developed further throughout the analysis process. In particular this level of analysis focuses on women's experience of POP and symptoms; experience of self-management/standard pessary care; perceptions of treatment and causes for POP; experience of trial participation; experience of recruitment process; perceptions of treatment outcomes; adherence to trial group (where applicable); reasons for declining participation in the main trial. At this stage, the analysis is aimed at identifying barriers and facilitators to adherence to trial group, acceptability of self-management pessary care and acceptability of trial participation.

2. The case (woman) (steps 6 and 7)

Case summaries will be written with a focus on creating an understanding of women's experience in our areas of interest: the problem (POP), the treatment (self-management vs standard care), adherence to trial group (where applicable); perceptions of treatment outcome and how these factors interact. Analysis at this stage will focus on identifying issues relating to changes over time and in developing theoretical propositions to guide subsequent analysis (Yin 2013).

3. The three different arms of the interview study (step 8)

All the cases for one arm of the interview study (intervention, control, non-randomised) will be collected together and consistencies/ inconsistencies searched for. The aim of analysis at this stage is to identify the core barrier and facilitators within the trial arms, as well as, detailed explanations for them and interactions between them. An additional degree of complexity will be added by including the cases from the non-randomised women as they can be self-managing or receiving standard care.

4. Across cases and different arms of the interview study (step 9)

The intervention and control arms of the trial will be compared to one another using the theoretical propositions of the study. The aim of this part of the analysis is to identify similarities and differences between the two trial arms with regards to barriers and facilitators. Additionally, cases from the non-randomised interview only arm will be compared to the trial arms with regards to experiences of treatment and perceptions of treatment outcome. This will be conducted by comparing the arm to each individual trial arm as a whole and by separating out self-management cases for comparison to the intervention arm, and standard care cases to the control arm of the trial.

Analysis will be shared with Qualitative PMG throughout the process. At the point at which the data can be shared with the wider team it will also be discussed with PMG and TSC. Finally it will be reported to HTA.

